11.10 SAFETY ANALYSIS

Safety will be monitored during the period starting after receipt of the first dose of study drug and ending 30 days after the final administration of alvocidib. During Phase 1, the safety endpoints will be evaluated after Cycle 1. The dose escalation committee will have access to complete safety profiles of all patients receiving alvocidib and will be able to take decisions accordingly.

All patients who receive any dose (any amount) of alvocidib will be included in the summaries and listings of safety data. Overall safety profile will be characterized by type, frequency, severity, timing, duration and relationship of study drug of adverse events and laboratory abnormalities.

11.10.1 Adverse Events

Adverse events will be classified using the MedDRA classification system version 20.0 or higher. The severity of the toxicities will be graded according to the NCI CTCAE v5.0.

In all summaries, emphasis will be placed on TEAEs, namely, those with initial onset or that worsen in severity after the first dose of alvocidib. Adverse events will be summarized by the frequency of patients experiencing TEAEs corresponding to body systems and MedDRA preferred term and by worst NCI CTCAE (v5.0) grade. Summaries will also be provided of treatment-related TEAEs, namely, those judged by the investigator to be related or likely related to alvocidib and/or combination regimens.

Adverse events resulting in discontinuation of alvocidib treatment or withdrawal from the study, Grade 3 or higher, serious adverse events, and deaths on-study will be tabulated.

All DLTs will be reported and the MTD and RP2D identified.

11.10.2 Laboratory Tests

Laboratory data will be summarized for the observed values at each scheduled assessment, together with the corresponding changes from baseline (the value obtained prior to dosing on Day 1 of Cycle 1) using descriptive statistics.

For those analytes with NCI CTCAE v5.0 severity criteria are specified, abnormal laboratory values will be summarized by shift tables displaying numerical values and percentages classified by Baseline grade (ie, grade prior

to dosing on Day 1 of Cycle 1) and maximum grade on treatment. All laboratory data will be presented in listings.

11.10.3 Vital Signs and Physical Examination Findings

Vital signs data will be summarized by the observed values at each scheduled assessment, together with the corresponding changes from baseline using descriptive statistics.

Physical examination findings will be presented in data listings.

11.11 INTERIM ANALYSIS

For Phase 1b, safety data will be monitored continuously per standard Phase 1 oncology study practices.

For Phase 2, because the Simon 2-stage minimax design will be employed, response rate data will be assessed after Stage 1 and Stage 2.

11.12 PHARMACOKINETIC ANALYSIS

Pharmacokinetic parameters will be estimated using standard noncompartmental methods and according to FDA guidance. PK parameters include:

- C_{\max} = maximum observed plasma concentration
- T_{\max} = time to C_{\max} (peak time)
- AUC_{0-24} = area under the plasma concentration curve from time 0 to 24 hours
- $AUC_{0-\infty}$ = AUC from time 0 to infinity
- AUC_t = area under the plasma concentration curve from time 0 to time t
- $t_{1/2}$ = half life
- CL = clearance using noncompartmental methods

Actual sample collection times will be used rather than scheduled collection times. Plasma concentrations below the limit of quantification will be treated as 0. Imbedded missing plasma concentrations (ie, missing values between two observed values) will be estimated using linear extrapolation. This is consistent with using the trapezoidal rule to calculate AUC. Other missing plasma concentrations will be excluded from calculations to estimate PK parameters.

11.13 PHARMACODYNAMIC ANALYSIS

Peripheral blood and bone marrow samples will be collected at protocol-specific time points to assess the effects of alvocidib when administered in sequence after DEC (***during dose escalation***) or AZA. Analyses may include, but are not limited to: correlation of complete response rates with BH3 profiling by flow cytometry with an emphasis on MCL-1 dependence, evaluating recurrent genetic mutations, and other biomarkers associated with MDS.

12. PROTOCOL AMENDMENTS

Any permanent change to the protocol must be handled as a protocol amendment. Protocol amendments will be written by the Sponsor. All protocol amendments must be submitted in writing to the Institutional Review Board (IRB)/Independent Ethics Committee (IEC), and the PI must await IRB/IEC approval of the amendments before implementing the changes. However, a protocol change which is intended to eliminate an apparent immediate hazard to patients may be implemented immediately, provided the IRB/IEC is notified within five (5) days. The Sponsor should also be notified by telephone as soon as possible, ideally before the amendment is implemented and definitely within 5 days. The Sponsor will submit protocol amendments to the Regulatory Authorities.

When an amendment to the protocol substantially alters the study design and/or increases the potential risk to the patient, the currently approved written informed consent form will require similar modification and IRB/IEC approval. In such cases, repeat written informed consent will be obtained from patients currently enrolled in the study before expecting continued participation.

13. MONITORING

Prior to enrolling any participants, a study initiation visit (SIV), including protocol training, will be conducted for the study center. A Study Manual of Procedures will be provided to each clinical site. A record of site personnel training will be maintained by the site onsite training logs.

Clinical Research Associates (CRAs) and other applicable personnel will receive training prior to study initiation about the disease, applicable Standard Operating Procedures (SOPs), the protocol and other study-specific items. Team organization, communication, and operational issues will also be discussed.

The conduct of the study will be closely monitored by representatives (Clinical Research Associates "CRAs" or study monitors) of the Sponsor or designee, to verify adherence to the Protocol, ICH GCP guidelines, and applicable regulations. The CRA will verify eCRF entries by comparing them with Sponsor/site-generated source documents, hospital, clinic, office and/or study records which will be made available for this purpose. CRAs will monitor the study as outlined in the Monitoring Plan prepared for the study.

During the study, CRAs will visit the clinical sites to assess and assure satisfactory enrollment rate, data recording, and maintenance of required regulatory documentation, drug accountability, and compliance with the protocol. CRAs will also be able to monitor the data remotely. The Investigator will ensure that all requested materials, including subject charts, eCRFs, source documents, laboratory records, and drug inventory records, will be available to the CRA. At the end of the study, a closeout visit will be performed.

The Investigator will allow Sponsor's representatives, designee and/or and any regulatory agency to have direct access to all study records, eCRFs, corresponding subject medical records, test product dispensing records and test product storage area, and any other documents considered source documentation. The Investigator also agrees to assist the representative, if required.

14. AUDITING

The study is conducted under the sponsorship of **Sumitomo Dainippon Pharma Oncology, Inc (SDP Oncology)**, in compliance with the applicable international and local regulatory requirements as well as applicable ICH guidelines, Declarations of Helsinki (1964, 1975, 1983, 1989, 1996, 2000, 2002, 2004, 2008, 2013) and in respect of the Sponsor or designee's standard operating procedures (SOPs) for study conduct and monitoring.

Audits may be carried out by Sponsor representatives, and inspection may be performed by regulatory authorities' inspectorate or IRBs/IECs before, during, or after the study. The Investigator will allow and assist Sponsor's representatives and any regulatory agency to have direct access to all study records, eCRFs, subject medical records, study product dispensing records and study product storage area, study facilities, and any other documents considered source documentation.

For the Audit(s) performed by, or on behalf of, Sponsor's auditors, audit findings will be provided by Quality Assurance, in writing.

15. ETHICS AND RESPONSIBILITY

15.1 PRINCIPAL INVESTIGATOR'S RESPONSIBILITIES

The PI shall ensure that all work and services described herein, or incidental to those described herein, shall be conducted in accordance with the highest standards of GCP. The PI shall administer the investigational drug only to patients under his/her personal supervision, or under the supervision of any Sub-Investigator(s) responsible to him/her, who are identified on the Form FDA 1572/Regulatory Authorities approval form. The PI will provide copies of the study protocol, amendments, and investigational brochure to all Sub-Investigators, Pharmacists, or other staff responsible for study conduct.

With the exception of eliminating an immediate hazard to a subject, the Investigator should not deviate from the protocol or implement any changes without written prior approval from Sponsor and prior review and documented approval/favorable opinion from the IRB/IEC of an amendment.

Change(s) which involve(s) only logistical or administrative changes are authorized. The Investigator should document and explain any deviation from the protocol.

The Investigator is responsible for adequate and safe medical care of subjects during the trial and for ensuring that appropriate medical care and relevant follow-up procedures are maintained after the trial. Any additional data from these follow-up procedures must be documented and available to Sponsor who will determine whether or not the data need to be documented in the case report forms.

15.2 INFORMED CONSENT

It is the ethical and legal responsibility of the PI to ensure that each patient considered for inclusion in this study is given a full explanation of the protocol, in a language in which the patient is fluent, and in which the patient will clearly understand. This shall be documented on a written informed consent form, which shall be approved by the same IRB/IEC responsible for approval of this protocol. Each informed consent form shall include the elements required by local regulations. The Sponsor will draft this document in consultation with the PI. The PI agrees to obtain written approval of the consent form from the Sponsor prior to submission to the IRB/IEC.

Once the appropriate essential information has been provided to the patient and fully explained by the PI (or his/her qualified designee) and it is felt that the patient understands the implications of participating in the study, the IRB/IEC-approved consent form shall be signed by the patient, a witness (when appropriate) and the PI (or designee). Written informed consent will be obtained from each patient prior to any study-related procedures (including any pre-treatment procedures) that are performed. The patient shall be given a copy of the informed consent form when signed; the original shall be kept on file by the PI and a second copy shall be placed in the patient's medical chart (or per EMR SOP).

15.3 INSTITUTIONAL REVIEW BOARD

This protocol and all amendments will be reviewed and approved by the Institutional or Independent Review Board(s) or Independent Ethics Committee(s) charged with this responsibility at the study center. Notification in writing of approval must come from the Chairman or the Secretary of the IRB/IEC meeting minutes where this protocol and associated informed consent form were discussed. The PI shall not participate in the decision, and, if an IRB/EC member, the written approval must indicate such non-participation. The PI shall submit status reports to the IRB/IEC no less frequently than annually (when applicable). The IRB/IEC must be notified by the PI in writing of the interruption and/or completion of the study; the PI must promptly report to the IRB/IEC all changes in research (protocol amendments) and will not make such changes without IRB/IEC approval, except where necessary to eliminate apparent immediate hazards to human patients. In these cases, the IRB/IEC must be notified within five days of the change. The PI will promptly report to the IRB/IEC all unanticipated problems involving risk to patients or others. The PI is required to maintain an accurate and complete record of all written correspondence to, and received from the IRB/IEC, and must agree to share all such documents and reports with the Sponsor.

17. NONPROTOCOL RELATED RESEARCH

The Sponsor has a legal responsibility to report fully to regulatory authorities all the results of administration of investigational drugs. No investigative procedures other than those in this protocol shall be undertaken on the enrolled patients without the agreement of the IRB/IEC and the Sponsor's medical monitor.

18. PUBLICATIONS

The publication policy for the study will be described in the clinical study agreement. To avoid disclosures that could jeopardize proprietary rights, the investigator agrees to give **SDP Oncology**, Inc, the right to review all manuscripts, abstracts, and presentations related to this study *prior* to their submission for publication or presentation. **SDP Oncology** may use these data now and in the future for presentation or publication at **SDP Oncology**'s discretion or for submission to government regulatory agencies.

Authorship among Investigators generally will be based on the extent of significant contribution, including scientific and clinical, to the publication.

APPENDIX A-1 – SCHEDULE OF ACTIVITIES (Patients Receiving DEC and Alvodidib)
Phase 1b, Expansion, and Phase 2

CYCLE DAY	PREDOSE		CYCLE 1					CYCLES 2+					END OF STUDY ^a	FOLLOW UP ^b
	-28 D	-72 HR	D1	D8	D9	D15 (±3d)	D22 (±3d)	D1	D8	D9	D15 (±3d)	D22(±3d)	D28 (+1/-3d)	
PROCEDURES/TESTS														
Signed informed consent ^c	X													
Medical / disease history ^d	X													
Complete physical exam	X	X											X	
Height (cm)	X													
Weight (kg)	X	X						X					X	
Transfusion dependency ^u	X													
Vital signs ^e	X	X	X ^q	X	X	X	X	X ^q	X	X	X	X	X	
ECOG PS	X	X		X		X	X	X	X	X			X	
12-lead ECG plus QTc	X													
Chest radiograph ('x-ray') ^f	X													
CBC w/ manual diff & pltts	X	X	X	X ^v	X	X	X	X	X ^v	X ^{gg}	X	X	X	
Serum chemistries ^g	X	X	X	X ^v	X	X	X	X	X ^v	X ^{gg}	X	X	X	
Coag panel: PT & aPTT	X												X ^{bb}	
Interim labs ^g	Laboratory assessments conducted at times other than per-protocol visits													
Pregnancy test ^h	X	X	X ^s					X					X	
BM biopsy/aspirate	X ⁿ												X ^z	X ^{cc}
PD blood sampling	X ⁿ		X ^{r,w}	X ^w	X ^w	X ^w	X ^w	X ^w	X ^w	X ^w			X ^{z,aa}	X ^{cc}
Concomitant medications ⁱ	X ^o	X ^p	X ^t	X ^t	X ^t	X ^t	X ^t	X ^t	X ^t	X ^t	X ^t	X ^t	X ^t	X ^{t,dd}
Calculate BSA		X						X						
Baseline signs / symptoms		X	X ^q											
Confirm eligibility ^j		X												
Standard TLS prophylaxis		X ^{bb}	X ^{bb}	X ^{bb}	X ^{bb}			X ^{bb}	X ^{bb}	X ^{bb}				
Administer prophylactic medications ^k			X	X				X	X					
Decitabine administration (1-hr IVI on Days 1-5)			X					X						
Assessment of AEs ^l			X	X	X	X	X	X	X	X	X	X	X	X ^{ee}
Abbreviated physical exam ^m				X	X	X	X	X	X	X				
Alvodidib administration ^{ff}				X					X					
PK blood sampling				X ^x	X ^y									

Notes:

- a. If, at any time, a patient discontinues study treatment, a visit should be scheduled as soon as possible and within 14 days of the last dose of study drug or within 14 days of the decision to discontinue study treatment. If the decision to withdraw the patient occurs at a regularly scheduled visit, that visit may become the End of Study visit rather than having the patient return for an additional visit.
- b. Patients must have a safety evaluation 30-45 days after the last dose of study drug (ie, 30 days +15-day window). This evaluation can be done by phone.
- c. Written informed consent must be obtained prior to conduct of study-related screening evaluations. Evaluations performed as standard-of-care prior to obtaining consent may be utilized for screening.
- d. Collect and document a complete medical and disease history including histologically confirmed diagnosis of MDS.
- e. Vital signs to include: temperature, heart rate, systolic and diastolic blood pressures.
- f. May omit if performed within 28 days prior to anticipated first dose.
- g. Full serum chemistry panel to include: blood urea nitrogen, phosphorus, magnesium, lactate dehydrogenase, creatinine, uric acid, total protein, albumin, calcium, glucose, total bilirubin, alkaline phosphatase, aspartate aminotransferase, alanine aminotransferase, and electrolytes (sodium, potassium, chloride, CO₂) (see *Appendix E*). All laboratory values for hematology and serum chemistry parameters collected during the time the patient is on study to facilitate change-from-baseline analyses. Any laboratory parameters assessed outside the per-protocol visits (ie, interim labs) will be recorded as 'Unscheduled Laboratory Assessments' in the database.
- h. Collect urine or serum sample for β-hCG pregnancy test in females of child-bearing potential.
- i. Including all prescription and nonprescription medications and nutritional supplements.
- j. Review all inclusion and exclusion criteria to determine if patient has met all eligibility criteria for enrollment into the study. Obtain Medical Monitor (or designee) approval to enroll patient.
- k. Including prophylactic antibiotics, antivirals, antifungals, antiemetics, antidiarrheals according to standard practices at each site.
- l. Toxicities will be assessed according to the NCI CTCAE v5.0 (see *Appendix D*). When the NCI CTCAE grade is not available, the investigator will use the following toxicity grading: mild, moderate, severe, life-threatening, or fatal.
- m. AE- or symptom-directed physical examination.
- n. Perform bone marrow biopsy and/or aspiration and collect peripheral blood for disease status, standard cytogenetics, and PD analyses (*Appendix E*). If the initial bone marrow aspirate is nonproductive or not diagnostic, the procedure must be repeated. Six to 8 bone marrow slides will be prepared (in addition to fresh bone marrow samples) and sent to the Sponsor.
- o. Including all prescription and nonprescription medications and nutritional supplements taken over previous 28 days.
- p. Including all prescription and nonprescription medications and nutritional supplements taken since previous predose assessment visit.
- q. Conducted just prior to first dose.
- r. Collect peripheral blood samples for PD analyses on Days 1, 3, and 5 of Cycle 1 within 10 minutes prior to decitabine infusion (Section 7.4, *Table 9; Appendix E*).
- s. Required if screening pregnancy test was performed >72 hours prior to first dose.
- t. Record only those medications (prescription, nonprescription, nutritional supplements) administered in conjunction with an AE.
- u. Collect and document transfusion dependency, ie, transfusion requirement without any consecutive 28-day gaps between transfusions for a minimum of 56 days immediately preceding first dose and/or hemoglobin level. **Record all transfusions (hemoglobin and platelet) for the 8 weeks/56 days prior to screening (including the transfusion date and number of units with each transfusion). Record all CBC data for the 8 weeks/56 days prior to screening including each CBC that prompted a transfusion.**
- v. Collect blood just prior to start of infusion and again approximately 4 hrs post end of IVI (Time 0 = start of alvocidib IVI).
- w. Collect peripheral blood for PD analyses (see Section 7.4, *Table 9; Appendix E*).

- x. **Phase 1b only** - Collect blood samples for PK analyses on Day 8 just before the alvocidib IVI (Sample #1) and at the end of the alvocidib IVI (Sample #2). The time between the end of the 30-min bolus and beginning of the 4-hr alvocidib IVI should be up to 30 mins. Continue to collect blood samples for PK analyses 30 mins after end of the alvocidib IVI (Sample #3), 1 hr after end of the alvocidib IVI (Sample #4), 2 hrs after end of the alvocidib IVI (Sample #5), and 4 hrs after end of the alvocidib IVI (Sample #6) (*Section 7.3, Table 8*).
- y. **Phase 1b only** - Collect a blood sample for PK analysis from all patients on Day 9 at 23 hrs after **the start** of the alvocidib IVI administered on Day 8 (Sample #7) (*Section 7.3, Table 8*).
- z. Perform bone marrow biopsy and aspiration and collect peripheral blood sample for assessment of response (*Appendix F*), standard cytogenetics, and PD analyses (*Appendix E*). [Note: with a +1/3 day window, these assessments may be performed on Days 25-28 or Day 1 of the next cycle. If performed on Day 1 of the next cycle, collect bone marrow and aspiration as well as peripheral blood samples prior to administering the first dose of decitabine.]

If the bone marrow biopsy and/or aspirate is nonproductive or not diagnostic, at the EVEN 2+ cycle visits, there should be no delay in dosing and the procedure should be repeated within 7 days. Six to 8 bone marrow slides will be prepared (in addition to fresh bone marrow samples) and sent to the Sponsor.

Response assessments and standard cytogenetics should be repeated on Day 28 (+1/-3 days) of Cycles 2, 4, and 6, and then every 4 cycles, thereafter, or as clinically indicated. If medically appropriate, response assessments should be repeated at the time of disease progression.

- aa Peripheral blood samples to be collected for PD analyses on Day 28 of even cycles **2, 4 and 6 and then every 4 cycles thereafter (ie, Cycle 10, Cycle 14, etc) or as clinically indicated** (*Appendix E*).
- bb As clinically indicated.
- cc If ≥ 8 weeks since last response assessment, perform bone marrow biopsy and aspiration and collect peripheral blood sample for assessment of response (*Appendix F*), and PD analyses (*Appendix E*). If the bone marrow biopsy and/or aspirate is nonproductive or not diagnostic, the procedure must be repeated within 7 days. Six to 8 bone marrow slides will be prepared (in addition to fresh bone marrow samples) and sent to the Sponsor.
- dd Including any antineoplastic therapies initiated since discontinuation of study drug.
- ee Ongoing AEs must be followed clinically until the event is resolved, deemed permanent or no longer clinically significant, or the patient begins an alternative treatment regimen.
- ff Alvocidib to be administered at the dosages noted in *Table 5* first as a (30-min [± 10 mins]) IV bolus followed up to 30 mins later by a 4-hr [± 15 mins] IVI.
- gg **After Cycle 3, frequency of labs may be performed as per standard of care starting after Day 9.**

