	
Cycle 1 in all patients enrolled in the Phase 1b study.
 
Cycle 1, Day 8 (DEC+ALV) / Cycle 1, Day 10 (AZA+ALV):
 
  
 PK Sample No.	Timepoint in Relation to Alvocidib Administration	Window	
   
 1	Prior to IVI	At any time	
 
 2	End of IVI	±10 minutes	
 
 Up to 30-minute wait (±10 minutes)^a	
 
 3	30 mins after end of IVI	±10 minutes	
 
 4	1 hr after end of IVI	+10 minutes	
 
 5	2 hours after end of IVI	±15 minutes	
 
 6	4 hrs after end of IVI	±15 minutes	
  
 
a This wait time is only required in patients receiving DEC followed by alvocidib hybrid dosing (ie, 30-min IV bolus; up to 30-min wait; and then the 4-hr IVI).
 
Cycle 1, Day 9 (DEC+ALV) / Cycle 1, Day 11 (AZA+ALV):
 
  
 PK Sample No.	Timepoint in Relation to Alvocidib Administration	Window	
   
 7	After alvocidib IVI (23 hrs after start of 4-hr IVI in pts receiving hybrid dosing or start of infusion in pts receiving 30- to 60-min IVI)	±1 hour	
  
				PK Sample No.	Timepoint in Relation to Alvocidib Administration	Window	1	Prior to IVI	At any time	2	End of IVI	±10 minutes	Up to 30-minute wait (±10 minutes) ^a			3	30 mins after end of IVI	±10 minutes	4	1 hr after end of IVI	+10 minutes	5	2 hours after end of IVI	±15 minutes	6	4 hrs after end of IVI	±15 minutes	PK Sample No.	Timepoint in Relation to Alvocidib Administration	Window	7	After alvocidib IVI (23 hrs after start of 4-hr IVI in pts receiving hybrid dosing or start of infusion in pts receiving 30- to 60-min IVI)	±1 hour																	
PK Sample No.	Timepoint in Relation to Alvocidib Administration	Window																																																	
1	Prior to IVI	At any time																																																	
2	End of IVI	±10 minutes																																																	
Up to 30-minute wait (±10 minutes) ^a																																																			
3	30 mins after end of IVI	±10 minutes																																																	
4	1 hr after end of IVI	+10 minutes																																																	

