7.3 PHARMACOKINETIC ENDPOINTS

Plasma concentrations of alvocidib will be summarized by descriptive statistics, including mean, n, standard deviation, coefficient of variation, minimum, maximum, and median. Prior to analysis of study samples, the assay sensitivity, specificity, linearity, and reproducibility will be documented.

Parameters to be assessed include the time to C_{max} (Peak time, T_{max}) and the area under the plasma concentration versus time curve (AUC) from time 0 to 24 hours post-dose (AUC_{0-24}), the maximum observed plasma concentration (C_{max}), half life ($t_{1/2}$), AUC from 0 to time t (AUC_t), AUC from time 0 to infinity (AUC_{0-inf}), and clearance (CL).

Plasma PK analyses for alvocidib and known metabolites, if any, and dose proportionality will be determined during Cycle 1 on Days 8 and 9 (in patients receiving alvocidib following DEC) or Days 10 and 11 (in patients receiving alvocidib following AZA) ([Table 8](#)).

Table 8: Timing of PK Sampling during Cycle 1 of Phase 1b Study

PK Sample No.	Day (Regimen)	Timepoint in Relation to Alvocidib Administration	Window
1	D8 (DEC + ALV) /	Prior to IVI	At any time
2	D10 (AZA + ALV)	End of IVI	+10 mins
Up to 30-min wait (\pm 10 mins) ^a			
3	D8 (DEC + ALV) / D10 (AZA + ALV)	30 mins after end of IVI	\pm 10 mins
4		1 hr after end of IVI	\pm 10 mins
5		2 hrs after end of IVI	\pm 15 mins
6		4 hrs after end of IVI	\pm 15 mins
7	D9 (DEC + ALV) / D11 (AZA + ALV)	After alvocidib IVI (23 hrs after start of IVI in pts receiving hybrid dosing or start of infusion in pts receiving 30-60 min IVI)	\pm 1 hr

ALV = alvocidib; AZA = azacitidine; DEC = decitabine; IVI = IV infusion

a This wait time is only required in patients receiving DEC following alvocidib hybrid dosing (ie, 30-min IV bolus; up to 30-min wait; and then the 4-hr IVI).

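### Hybrid alvocidib has two concentration peaks but only one end-of-dose PK sample, and the text does not settle which peak that sample covers

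*Protocol*

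**What the plan says.** Hybrid dosing is defined the same way throughout. The Synopsis PK footnote gives the sequence as "30-min IV bolus; up to 30-min wait; and then the 4-hr IVI". Protocol 2.6, 4.4.2 and Appendix A-1 note ff keep the bolus and the 4-hour IVI apart as two separate inputs.

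Appendix A-1 note x places the first two PK draws "just before the alvocidib IVI (Sample #1) and at the end of the alvocidib IVI (Sample #2"). Its next sentence is "The time between the end of the 30-min bolus and beginning of the 4-hr alvocidib IVI should be up to 30 mins", and then "Continue to collect blood samples for PK analyses 30 mins after end of the alvocidib IVI (Sample #3"). Samples 4 to 6 follow at 1, 2 and 4 h after the end of the IVI, and Sample 7 is 23 h after its start.

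Table 8 (Protocol 7.3) and the Synopsis table also label Sample 2 as the end of the IVI, and also set a row, "Up to 30-min wait", between Samples 2 and 3. Both let Sample 1 be drawn at any time before the IVI.

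Protocol 11.12 promises observed Cmax, Tmax, trapezoidal AUC and "CL = clearance using noncompartmental methods", using actual collection times. Protocol 7.3 and SAP 13 add dose proportionality. SAP 18 repeats note x without resolving it.

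**The concern.** Two inputs produce two local peaks, one at the end of the bolus and one at the end of the 4-hour infusion. The schedule has one end-of-dose sample. If Sample 2 follows the infusion, as the word IVI implies, nothing is drawn at the end of the bolus. If it follows the bolus, as the position of the wait implies, the first draw after the infusion is 30 minutes late. Sites could apply either reading under the same sample number.

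A noncompartmental Cmax is an observed maximum, so a peak that was not sampled cannot be recovered. The bolus also carries 20/40 = 50% of the dose at Levels 1-2 but only 30/90 = 33% at Level 4. An error that depends on the bolus share therefore changes with dose level and can look like non-proportionality.

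**Working it through.** **Who is affected.** SAP section 1 gives Cohorts 1-4 as 3+3+3+4 = 13 of 20 patients. Cohorts 5-6 received a single 30- to 60-minute infusion, which the schedule fits.

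**Inputs.** Doses D1/D2 (bolus/infusion, mg/m²) are 20/20, 30/30, 30/45 and 30/60 (Protocol Table 5). Durations are 0.5 h and 4 h, with wait w = 0.5 h. Assumed: one compartment, linear kinetics, volume 1. The documents give no human half-life, only 1.1 h (dog) and 1.9 h (rat) in Protocol 2.4.3, so I use 1.1-6 h.

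**Peaks**, with k = ln 2 / half-life:
- end of bolus: Cb = D1/(0.5k) × (1 − e^(−0.5k))
- end of infusion: Ci = Cb × e^(−k(w+4)) + D2/(4k) × (1 − e^(−4k))

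At 1.1 h, k = 0.630:
- Level 1: Cb = 17.16 and Ci = 1.01 + 7.30 = 8.30. If only Ci is sampled, Cmax is 8.30/17.16 = 0.48 of true.
- Level 4: Cb = 25.73 and Ci = 1.51 + 21.89 = 23.40, ratio 0.91.

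The peaks are equal at a half-life of about 2.8 h (Levels 1-2), 1.8 h (Level 3) and 1.25 h (Level 4). Below that the bolus peak is the higher.

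**AUC, Level 1 at 1.1 h.** True AUC is 40/0.630 = 63.5, with a negligible remainder at 24 h. Using linear-up/log-down:
- Sample 1 pre-bolus, Sample 2 at end of IVI: triangle 5 × 8.30/2 = 20.8, tail 8.30/0.630 = 13.2; total 33.9, or 0.53 of true.
- Sample 1 just before the IVI (12.52), zero taken at time 0, Sample 2 at end of IVI: 6.3 + 41.1 + 13.2 = 60.5, or 0.95.
- Sample 2 at end of bolus, next draw 30 minutes after the IVI (6.06): 4.3 + 53.3 + 9.6 = 67.2, or 1.06.

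**Across the range** (ratios to true, log-down AUC). Reading A: Sample 1 pre-bolus, Sample 2 at end of IVI. Reading A′: Sample 1 just before the IVI, Sample 2 at end of IVI. Reading B: Sample 2 at end of bolus.

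| Half-life | Level | Cmax A | Cmax B | AUC A | AUC A′ | AUC B |
|---|---|---|---|---|---|---|
| 1.1 h | 1 | 0.48 | 1.00 | 0.53 | 0.95 | 1.06 |
| 1.1 h | 4 | 0.91 | 1.00 | 0.67 | 0.92 | 0.97 |
| 1.9 h | 1 | 0.77 | 1.00 | 0.67 | 0.96 | 1.01 |
| 1.9 h | 4 | 1.00 | 0.83 | 0.78 | 0.94 | 0.96 |
| 3 h | 1 | 1.00 | 0.96 | 0.78 | 0.96 | 0.99 |
| 3 h | 4 | 1.00 | 0.89 | 0.86 | 0.96 | 0.97 |
| 6 h | 1 | 1.00 | 0.94 | 0.88 | 0.98 | 0.99 |
| 6 h | 4 | 1.00 | 0.94 | 0.93 | 0.98 | 0.99 |

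Under A′, Cmax at Level 1 and 1.1 h is 12.52/17.16 = 0.73. CL errs by the reciprocal of the AUC ratio: under A, 1/0.93 = 1.08 to 1/0.53 = 1.9 times true. With no wait the pattern is the same (A from 0.52; the others 0.91-1.07).

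**Apparent non-proportionality.** With exactly linear kinetics, dose-normalised AUC under A rises from Level 1 to Level 4 by 25% at 1.1 h (0.67/0.53), 17% at 1.9 h and 11% at 3 h.

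**The case against.** A reader might infer that note x and Table 8 contradict each other. They do not: both call Sample 2 the end of the IVI, both put the wait after it, and note x cites Table 8. The tension lies inside each text, between its term and its order, so the schedule is ambiguous rather than contradictory.

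A reader might also infer that Cmax, Tmax, AUC and CL are all underivable for these patients. That does not follow either. Under the end-of-IVI reading Cmax and Tmax are exact in the model at 3 h or more; under the end-of-bolus reading Cmax is exact whenever the bolus peak is the higher. AUC is badly off mainly under reading A. A factor-of-two gap in AUC between readings is a corner case: 1.06/0.53 = 2.0 at Level 1 and 1.1 h, but 0.99/0.78 = 1.3 at 3 h and 0.99/0.88 = 1.1 at 6 h.

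Linear trapezoids would add error from the long gap before Sample 7 under any of these schedules. That error is not due to a missed peak, which is why log-down is used above. Protocol 11.12 does not say which rule applies.

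The impact is also limited. PK is not a Phase 1b objective (Protocol 3.1). SAP 13 calls it exploratory and allows it to be left out of the report. The MTD rests on DLTs. Enrolment closed on 17 November 2020, and the planned later phases do not use hybrid dosing.

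All of this stands. What remains is that no reading samples both peaks, and the SAP still plans these parameters and dose proportionality without saying what to do about it.

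**Conclusion.** The concern holds as an unresolved sampling ambiguity affecting 13 of 20 patients. One peak is unsampled on either reading, and the position of Sample 1 relative to the bolus is open.

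- **Cmax and Tmax** are wrong when the missed peak is the higher. For half-lives of 1.1-6 h, Cmax is 0.48-1.00 of true if Sample 1 is pre-bolus and Sample 2 ends the infusion, and 0.83-1.00 if Sample 2 ends the bolus.
- **AUC and CL** are materially biased mainly with a pre-bolus Sample 1 and an end-of-IVI Sample 2 (AUC 0.53-0.93 of true, milder at longer half-lives). That bias shrinks as the bolus share falls, so it can mimic non-proportionality. Otherwise AUC is about 0.92-1.06 of true.

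These sizes rest on the assumed one-compartment model and half-life range, a 0.5 h wait and the log-down rule; they illustrate and do not predict. The consequence is confined to exploratory PK.

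**What to change.** **SAP, for the 13 patients already sampled (the operative change).** Classify Samples 1 and 2 by actual clock time against the recorded bolus and IVI start and stop times. Do not report noncompartmental Cmax or Tmax for a hybrid patient with an unsampled peak. Do not report AUC, CL or dose proportionality where no sample lies after the start of the bolus and before the end of the IVI. State the trapezoid rule. A compartmental model using both recorded inputs is optional. The cost is SAP wording and a data check, with no new blood draws.

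**Schedule texts.** Reconcile note x, Table 8, the Synopsis table and SAP 18 so that each sample names the dose part it follows and time 0 is the start of the bolus. Also reconcile the printed windows: Sample 2 is ±10 minutes in the Synopsis and +10 in Table 8; Sample 4 is +10 and ±10. The footnotes differ too: "This wait time is only required in patients receiving DEC following alvocidib hybrid dosing" in Table 8 against "This wait time is only required in patients receiving DEC followed by alvocidib hybrid dosing" in the Synopsis.

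**If hybrid dosing is sampled again.** Within the same seven draws, include pre-bolus, end of bolus, just before the IVI and end of the IVI, then 1 h and 4 h after its end and 23 h after its start. In the same model Cmax is then exact and log-down AUC is 0.97-1.04 of true. The cost is two fewer early post-infusion points (30 minutes and 2 h). The AUC gain over the end-of-bolus reading is small; the gain is in Cmax, Tmax and a single reading for all sites.
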